Milan, 6th August 2013

Effectiveness of mirror therapy in upper limb rehabilitation early after stroke

Introduction

Stroke is one of the major causes of disability in occidental world (1-3) and upper limb paresis is among the most disabling consequences (4). Intensive rehabilitation programs, especially if started early, may promote upper limb functional recovery (5-6) and cortical reorganization (7-9). However, when the sensory-motor deficit is severe, intensive rehabilitation programs are difficult to bring to a successful conclusion. The reduction of the patient's active motor participation alters the cortical representation of the involved limb and interferes with the recovery induced by neurorehabilitation. A rehabilitation program, based on the stimulation of the mirror neuron system, could provide a valid way to deal with and partially overcome these limits (9-13).

Mirror neurons, in particular those of the parietal-frontal network, are activated not only when a movement is performed, but also by the act of observing a motor action performed by others (14). It has been noticed that the activation of the premotor cerebral areas determined by the observation of a motor act, can foster a facilitating effect on the activation of the brain areas responsible for the execution of the same movement (14-17).

Mirror Therapy (MT) is a rehabilitation approach that uses a mirror placed aside the patient's trunk, hiding the paretic upper limb and reflecting the contralateral healthy arm. In this way, moving one half of the body and looking into the mirror, it is possible to have the illusion that gestures are carried out by the contralateral half, covered and not visible. Specifically, in pathological conditions, such as hemiparesis, the mirror covers the injured limb and reflects the sound one. In this way, when moving the sound hand, the patient sees his/her impaired limb moving. MT was first tested in phantom pain treatment with excellent results (18).

Subsequently, thanks also to the new scientific assumptions offered by the discovery of mirror neurons, attempts were made to apply MT also in post-stroke neurorehabilitation, both for upper limb motor recovery and for the treatment of spatial neglect (19-25).The studies conducted so far have yielded interesting results, however only a few works have been performed with a significant number of participants and with appropriate experimental designs. Among the most important works, Yavuzer and colleagues (21) completed a study on 40 post-stroke patients in the subacute phase (within 12 months after stroke), reporting a better recovery on upper limb function in patients treated with MT compared to untreated patients. In another randomized trial involving 36 patients, Dhole and colleagues (19) showed that even in the post-acute phase (starting from 6 weeks after stroke), MT seemed to induce a greater recovery of upper limb function in patients with severe hemiparesis. In this study, no effects of MT on spatial neglect, nor an impact of the presence of spatial neglect on motor recovery using MT were found. However, according to Ramachadran and colleagues (20) and to our working group (21), spatial neglect can have an impact on the ability to observe a body image reflected into a mirror and, consequently, on the correct execution of a MT protocol.

In conclusion, although the results obtained so far using MT are encouraging, an optimal MT protocol for patients with hemiparesis, who can present or not spatial neglect, is not available. Furthermore, although there are many evidences regarding the efficacy of starting neurorehabilitation immediately after a cerebral accident, no studies on MT have been performed in the early post-acute phase.

Aim

The aim of the present study is to demonstrate the efficacy of MT in a selected group of patients and to propose an optimal protocol for treatment specifically designed for this clinical population. Thanks to a targeted recruitment and to the accurate control of various clinical-instrumental variables that can play a decisive role in the effectiveness of a rehabilitative therapy, it will be possible to demonstrate the efficacy of MT in the functional recovery of the hemiplegic patient. The primary objective focuses on the motor recovery of the upper limb. We also propose as a secondary objective to demonstrate that MT can promote a global functional improvement of the patient in daily living activities.

Materials and methods

Trial design

Single-blind, randomized controlled trial with the aim of evaluating the effect of MT, added to a standard neurorehabilitation protocol, in a selected population of post-acute patients.

Participants

We will consecutively recruite all post-stroke patients admitted to our neurorehabilitation clinic.

Inclusion criteria are as follows:

- Ischemic/hemorrhagic stroke, which determines hemiparesis or hemiplegia.
- Time post onset no longer than 4 weeks
- Age between 18 and 80 years.
- First stroke or stroke recurrence without previous functionally evident motor outcomes.
- MMSE (Mini Mental State Examination) ≥ 24 (29-30)
- Absence of global aphasia. Comprehension deficit, when present, should be minimal, mild or moderate (Token Test score, Aachener Aphasie Test < 40) (33-34)
- Spatial neglect (can be present or not)
- Ideomotor apraxia (can be present or not)
- No other pathologies (e.g., upper limb joint-muscle) that could interfere with motor recovery
- No other seriously invalidating clinical conditions (cardiopathies, bronco pneumopathies)

The recruitment will take place according to the following specifications: during the daily clinical briefing of each Operative Unit of our Centre, physicians inform the physiotherapist coordinators about the patients admitted for post-stroke hemiparesis and coordinators, in turn, inform the physician and the physiotherapists responsible for the study.

1- Clinical Screening

The Medical Specialist in charge of the project will: (i) verify that the patients accomplish with the clinical and neuroimaging inclusion criteria in order to access the study; (ii) obtain the informed consent signed;

(iii) fill in the registration form and (iv) refer the patient to the neuropsychologist responsible for the project.

2- Neuropsychological screening with integrated cognitive evaluation

The neuropsychologist will perform a deep cognitive evaluation investigating: global cognitive functioning (Mini Mental State Examination) (29-30); presence of aphasia (Token Test, Aachener Aphasie Test, 33-34; oral naming, Batteria per l'Analisi dei Deficit Afasici, 35); spatial neglect (line and bell cancellation, 31-32; , 38; complex figure copy 39, 40; clock drawing test, 40; test for personal neglect, 41); ideomotor apraxia (movement imitation test, 36), and mood disorders (Hamilton Depression Rating Scale, 37). Patients will be randomly assigned to the MT or control group (CT).

Interventions

Treatment:

During the study period and regardless of randomization, patients will perform a standard rehabilitation program consisting of neuromotor therapy, physics, occupational therapy, speech therapy and cognitive rehabilitation, according to the patient's clinical needs.

The patients included in the MT group will complete a structured protocol lasting for 45 minutes a day, for a minimum of 30 days. Patients will have to execute movements of increasing complexity using the non-paretic upper limb:

Simple movements - with the pronated forearm: flexion-extension of the elbow, flexion-extension of the wrist, flexion of the wrist with proximal and distal extended fingers, opening and closing of the fist, finger tapping;

Complex movements- with the elbow flexed at 45° or flexed and lifted from the table: for example flexionextension of the fingers, closing of the fist, finger tapping, flexion of the forearm on the arm with simultaneous prone-supination of the forearm itself;

Functional movements - that consist in taking, lifting or moving objects of variable shape and weight: a pen, a plastic cup, a full aluminum can, a playing card, a tennis ball, a ball, a coin, all according to the instructions of the operator.

During the execution of the exercises the patients have to look at the movements performed in the mirror. At the same time they instinctively should imagine that they are executing those movements with the paretic upper limb.

Patients included in the Control Therapy (CT) will perform for 45 minutes a day, for a minimum of 30 days a protocol of exercises similar to that performed by the MT patients, but with a non-reflecting surface, in place of the mirror.

The physiotherapist will monitor the patients' level of attention during the course of the MT (concentration in looking in the mirror) giving a score between 0 (no attention) and 2 (maximum attention). If in the first two weeks of treatment (or 10 sessions) the total score of the attention scale is < 6, the patient will exit the

trial, unless there will be a clear trend of improvement in attention levels in the last sessions. Records of patients that will not show a sufficient level of sustained attention during therapy will be consider in the analysis of possible factors that affect the efficacy of MT rehabilitation. The mirror intervention both for the study group and for the control group will be in add-on modality and standard rehabilitation activity will be regularly plan.

Outcome measures

Functional evaluation

Four physiotherapists, after performing a joint training of 2 months, will deal alternatively and on randomized assignment with the functional assessment or treatment. Therefore, the physiotherapist who deals with the treatment will not be the same that will evaluate the patient both at T0 (baseline) and at T1 (after treatment).

The functional evaluation performed at T0 and T1 will be based on the following scales, which will constitute the outcome measures.

- Fugl-Meyer Asessment (FMA): a specific complex scale for stroke. In our study, we will use a part of the scale, specifically the 33 items used to evaluate motor function, coordination, somatic sensitivity and excursion of the joints of the upper limb (27). The administration of the scale will involve the execution of gestures with increasing complexity, pure or finalized engines. The score is based on the direct observation of the patient's performance in relation to the latter's ability to complete the item (score 2), to partially execute it (score 1), not to do it at all (score 0). The final score is given by the sum of the scores of all the items (from 0 to 66). The administration of the scale takes 35-40 minutes.

- Action Research Arm Test (ARAT): scale for the study of the functionality of the upper limb. It consists of 19 items grouped into 4 subtests (28). The items allow analysing both simple and finalized motor acts with variable difficulty. The score is based on the direct observation of the patient's performance: from the ability to complete the task on time (score 3), to the possibility of completing the task in a longer time than expected (score 2), to perform the task in an incomplete way (score 1), up to the total impossibility to complete the task (score 0). The score can therefore be between 57 and 0. The administration of the scale takes 10 minutes.

- FIM (Functional Independent Measure): 18-voice scale that analyses different activities of daily life. The score in each item varies from 1 (complete dependence) to 7 (complete self-sufficiency), thus offering a cumulative score and a score profile in the various items. In this way the degree of self-sufficiency in performing elementary functional activities such as personal care, sphincter control, mobility, locomotion (motor area) and communication and social interaction (cognitive area) is measured. The administration of this scale will take about 10 minutes.

The primary outcome consists in the motor recovery of the upper limb, evaluated using the Fugl-Meyer scale (27). Secondary outcome are a specific physiatrist scale for the upper limb, the Action Research Arm Test (ARAT, 28), and a generic functional scale, the Functional Independent Measure (FIM, 26).

Sample size and randomization

Data analysis will be performed by a biostatistics, blind with respect to the treatments performed. The sample size will be constituted of 40 patients (randomized in 20 for the experimental group, MT, and 20 for the control group, CT).

Randomization will be performed according to the block randomization procedure, which allows to balance the quantitative asymmetry of the patients assigned to the two groups. The "block" is a sequence of the randomization list, which contains the same number of patients to be assigned to patients treated with MT and to controls (CT). For example, a block of 4 generates six different sequences, each of which assigns two patients to the MT group and two to the CT: MT-MT-CT-CT, MT-CT-MT-CT, CT-CT-MT, CT-MT-CT-MT, MT-CT-CT-MT, CT-MT-MT-CT. Thanks to the progressive balanced assignment, block randomization guarantees a similar number of patients enrolled in the two groups.

Statistical analysis

It was calculated to have a power of 0.80 and to demonstrate an effect size of .90 (difference between the two treatments equal to 90% of the variability of the phenomenon) to a Student t test for independent data, performed at a significance level of 0.05 (two-tailed test).

Considering that the model of the analysis of covariance (ANCOVA), used for inferential analysis, has a greater expected efficiency (less residual variability) of at least 30%, it can be considered that the aforementioned sample size will allow to highlight also an effect size of around 0.7. The variables will be described by mean, median, standard deviation (quantitative variables) and absolute frequency and relative percentage (qualitative variables). Furthermore, for the differences between before and after treatment for the variables detected for each group, the 95% confidence intervals will be calculated. The analysis of the main and secondary variables will be carried out by analyzing the covariance (satisfied assumptions) with the base value as a covariate, the treatment group as a factor and inserting the variables relevant to the response to the treatment, which presented an unsatisfactory balance between the two groups at baseline. The effectiveness of the therapeutic intervention will be reported also in terms of effect size (difference between the variations of the scores in each group in relation to the total variance).

Expected results

The functional outcomes of stroke and the pathophysiological characteristics of the patients affected can be extremely variable. The standardization of patient groups is an extremely delicate moment in the design of efficacy studies of rehabilitation treatments. We believe that in this study a scrupulous standardization of the sample, the process of randomization, the separation of information between those responsible for patient assessment and data processing and analysis, may be the appropriate approach for the study of a correctly selected and homogeneous population.

Indeed, MT presents the scientific and physiological assumptions to positively impact on the patient's functional recovery with post-acute early-onset stroke. However, in order to highlight this aspect, it is necessary that the treatment is designed in strict relation with the patient's characteristics and that possible biases and interfering factors are carefully controlled.

Hopefully, with the careful execution of the proposed study design, it will be possible to demonstrate the efficacy of MT in the functional recovery process of the paretic upper limb of hemiplegic patients. This effective results will be expressed through the score improvement of the specific scales employed in the study.

Bibliography

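### Patients can leave the trial after randomisation on an attention score defined only for the mirror, and the plan neither requires their T1 nor says whether they enter the primary ANCOVA

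*Combined protocol and SAP*

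**What the plan says.** Allocation closes the screening procedure (Participants, neuropsychological screening): "Patients will be randomly assigned to the MT or control group (CT"). Everything below therefore happens after randomisation.

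Under Interventions, Treatment, MT is a protocol "lasting for 45 minutes a day, for a minimum of 30 days". CT does similar exercises "but with a non-reflecting surface, in place of the mirror". The physiotherapist monitors the "level of attention during the course of the MT (concentration in looking in the mirror") on a scale from 0 to 2. If in the first two weeks, or 10 sessions, "the total score of the attention scale is < 6, the patient will exit the", the sentence continues, "trial, unless there will be a clear trend of improvement in attention levels in the last sessions". On what happens to the data, the plan says: "Records of patients that will not show a sufficient level of sustained attention during therapy will be consider in the analysis of possible factors" affecting MT efficacy. The next sentence reads "The mirror intervention both for the study group and for the control group will be in add-on modality".

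Outcome measures places T0 at baseline and T1 once treatment is over, and says that the treating physiotherapist is not the assessor. Sample size and randomization fixes 40 patients, 20 per arm, without mentioning exits. Statistical analysis specifies an ANCOVA on baseline and treatment group, plus relevant variables found imbalanced at baseline. It does not say which patients enter it and gives no method for missing T1.

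**The concern.** A randomised comparison is protected only while the patients compared are those who were randomised. Here a patient can leave because of behaviour observed during treatment, as judged by a physiotherapist who can see which surface is in use, with an exception that has no numerical definition. The separate assessor and the blinded statistician do not control who leaves.

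The score is defined by looking into a mirror that CT does not have, so exits may fall in one arm only. T1 is tied to the end of a treatment of at least 30 days, so a patient who stops at about two weeks has no defined T1. If that assessment is not made, no later analysis can recover it.

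Exits are foreseeable. Neglect is allowed at entry, and the Introduction says that it can affect how patients observe a mirror image. The Introduction also reports a trial in which neglect had no impact on motor recovery with MT, so the documents do not settle whether those who leave would recover differently.

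**Working it through.** **Plan's own figure.** Effect size 0.90, power 0.80, two-sided 0.05 (Statistical analysis). n per arm = 2(1.960 + 0.842)²/0.90² = 19.4, so 20 per arm and 40 in total. This reproduces. The exact t test gives power 0.792 at 20 v 20. Nothing is added for exits.

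**The threshold.** Scoring frequency is not stated. If it is once per session (an assumption), the maximum over 10 sessions is 10 × 2 = 20, and a total below 6 is an average below 6/10 = 0.6 out of 2.

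**Bias if MT patients who exit are left out.** Exit rate and attention–outcome correlation are not in the documents, so they are assumed: 20 per arm, no true effect, baseline explaining 30% of T1 variance, and correlation ρ of 0.3 to 0.5 between attention and the part of T1 that baseline does not explain. With a fraction p of MT removed below a cut-off,

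bias = √0.7 × ρ × φ(z_p)/(1 − p), in SD of T1.

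- 2 of 20 (p = 0.1, φ = 0.1755): 0.8367 × 0.3 × 0.1755/0.9 = 0.049; with ρ = 0.5, 0.082.
- 4 of 20 (p = 0.2, φ = 0.2800): 0.8367 × 0.3 × 0.2800/0.8 = 0.088; with ρ = 0.5, 0.146.

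Simulation of the ANCOVA (40,000 null trials per setting, lowest-attention MT patients removed) agrees closely:

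| MT exits left out | Spurious difference | Two-sided type I error |
|---|---|---|
| 2 of 20 | about 0.05–0.08 SD | about 5.4–6.3% |
| 4 of 20 | about 0.08–0.14 SD | about 6–8% |

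With negative ρ the shift has the same size but goes against MT. With ρ = 0 there is no bias and the error stays at about 5%. With everyone kept, likewise.

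**Both arms.** If the same fixed cut-off acts in the same way in both arms (expected 4 exits each, ρ = 0.5), there is no bias and type I error is about 5%. Equal counts alone are not enough: the selection mechanism has to be the same.

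**Precision, with exits unrelated to outcome, effect size 0.90.** Noncentral t with noncentrality d√(n₁n₂/(n₁ + n₂)). For the t test d = 0.90. For the ANCOVA d = 0.90/√0.7 = 1.076, reading the plan's 30% gain as residual variance, with one further degree of freedom spent.

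| Analysed | t test | ANCOVA |
|---|---|---|
| 20 v 20 | 0.792 | 0.912 |
| 16 v 20 | 0.741 | 0.875 |
| 16 v 16 | 0.693 | 0.837 |

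Simulating the ANCOVA, which also allows for chance baseline imbalance, gives 0.903, 0.867 and 0.825. Power falls in each case, but the planned analysis stays above 0.80 at this effect size.

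**The case against.** Several points on the other side are fair.

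- *The plan does not discard these patients.* It says that their records will be considered in the analysis of factors affecting MT efficacy, which arguably needs an outcome, and the T0/T1 description makes no exception for exits. This stands as far as it goes: a reader might infer that these patients are excluded from the ANCOVA, and no sentence says so. Equally, none requires their T1 or places them in the primary comparison, and leaving the trial points the other way.
- *The rule may apply in both arms.* A reader might infer that only MT patients can exit. The sentence on add-on delivery speaks of the mirror intervention in both groups. It does not define a CT score, so the matter is open.
- *Exits may be few.* MMSE must be at least 24, the threshold is low if scoring is once per session, and improving patients stay. This is plausible but not established. With 2 exits the bias is small, and the figures near 8% need 4 exits, all from MT, ρ = 0.5, and exclusion.
- *The direction is unknown.* A reader might infer that the result would be tilted towards MT. That needs inattentive patients to recover less, which the documents do not establish.
- *Power survives.* A reader might infer that exits take the trial below its planned 0.80. The t test is already at 0.79 with nobody lost, and the planned ANCOVA stays above 0.80 at effect size 0.90 in the cases shown.
- *Covariate adjustment will deal with it.* It cannot be relied on. Attention is measured after baseline, and the rule for adding imbalanced variables has no threshold.

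**Conclusion.** The omission is certain from the text: a post-randomisation exit rule, a score defined only for the mirror, no T1 required after exit, and no analysis set. Following the plan can therefore lose primary outcomes selectively, possibly by arm.

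The consequence is not certain. The bias figures in the working rest on assumed exit counts and correlations and on exit from MT only with exclusion. They can be positive, negative or zero, and they vanish if the same selection acts in both arms. At their largest, 0.14 SD for 4 exits, they are about a fifth of the smaller design effect of 0.7 (0.14/0.7 = 0.20). The loss of precision is real but secondary.

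This is a cheap improvement, worth making because T1 cannot be recovered afterwards. It is not a demonstration that the trial's result would be wrong.

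**What to change.** 1. *Interventions, Treatment, and Outcome measures.* State that a total attention score below 6 does not end outcome follow-up. Collect T1 (FMA, ARAT, FIM) on patients who exit, at the time it would have been due had they continued. The sponsor needs to say when that is, since only a minimum duration is given. T1 for patients who complete treatment stays as planned; one fixed date for everyone would re-time the endpoint for those treated beyond 30 days and is not needed.
2. *Statistical analysis.* State that the primary ANCOVA includes all randomised patients in the arm assigned, report missing T1 by arm with the reason, and label any analysis of attentive patients only as secondary.
3. *Interventions.* Reconcile the attention-scoring text with the sentence on the mirror intervention in both groups: does the score and exit rule apply in CT and, if so, what is scored there? Whether sessions stop is for the sponsor to decide.

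Cost: a few sentences, plus 55 to 60 minutes of assessment per exited patient by the plan's own timings (FMA 35–40, ARAT 10, FIM 10). The downside is that the estimate then describes assignment to MT and may be smaller than the effect in attentive patients; the secondary analysis covers that question.

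### Does the plan leave the Fugl-Meyer rater unblinded, so that the primary comparison is at risk?

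*Combined protocol and SAP*

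**What the plan says.** Trial design describes a "Single-blind, randomized controlled trial with the aim of evaluating the effect of MT" and names no blinded party. Under Outcome measures, Functional evaluation, four physiotherapists train jointly for 2 months and then "will deal alternatively and on randomized assignment with the functional assessment or treatment". The next sentence draws the consequence: "the physiotherapist who deals with the treatment will not be the same that will evaluate the patient both at T0 (baseline) and at T1".

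The primary outcome is the upper-limb Fugl-Meyer score, 0 to 66. Each of its 33 items is scored 0, 1 or 2 from what the rater sees.

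Under Interventions, controls do similar exercises "but with a non-reflecting surface, in place of the mirror", and the physiotherapist giving the sessions scores attention to the mirror. Random assignment is mentioned at the end of the neuropsychological screening step. T0 appears only under Functional evaluation, where it is called baseline.

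Sample size and randomization states that the biostatistician is blind. Expected results mentions keeping information separate between those who assess patients and those who process and analyse data. Statistical analysis specifies ANCOVA with the baseline value as covariate.

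**The concern.** Barring self-rating controls who scores a patient. It does not in itself control what the scorer knows. If the four physiotherapists rotate between the two roles, each rater also delivers trial sessions to other patients. The arms differ by a visible object, so a glimpse of a session or its record would reveal the arm. The separation described in Expected results lies between assessment and data handling, not between raters and allocation. Read literally, the single-blind label could be met by the analyst alone.

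What would be at stake is expectation bias in an observer-scored primary outcome, which no analysis can remove afterwards. T0 might also be scored with the arm known, and T0 is the ANCOVA covariate.

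**Working it through.** **1. What the text supports.**

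- *Who is blinded.* The patient sees either a mirror or a non-reflecting surface. The treating physiotherapist sets it up. The analyst's blinding is stated separately. A trial labelled single-blind that also separates treater from evaluator for every patient, at both visits, is most naturally read as blinding the evaluator. The separation would have little other purpose.
- *Whether raters treat trial patients.* The role sentence has two readings. Roles may rotate; with an even split, each physiotherapist would then rate 40/4 = 10 patients and treat 10 others. Or each may be assigned at random to one role. Rotation is likelier, but the next sentence opens with a word of consequence, and its conclusion follows directly from fixed roles. Rotation is therefore an assumption.
- *Whether raters see arm-revealing material.* No section says that they attend sessions or read session records. The attention score is given by the physiotherapist monitoring the sessions. Its stated uses are exit from the trial and the analysis of factors affecting efficacy.
- *Rater leniency.* Random assignment of roles and joint training keep individual severity or leniency from lining up with arm.

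**2. The plan's own figure.** Inputs from Sample size and randomization and Statistical analysis: 20 per arm, effect size 0.90, two-sided 0.05. The noncentral t with 38 df gives power 79.2%, and the normal approximation 81.2%. The stated 0.80 is reproduced and does not depend on rater blinding.

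**3. Illustration of a rater shift.** The documents give no figure for such a shift. Assume b = 0.1, 0.2 or 0.3 SD in favour of mirror therapy, with no true effect.

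The chance of a significant result comes from a noncentral t with noncentrality (net shift / residual SD) × √(20/2). The t test uses 38 df and ANCOVA 37. The plan's 30% reduction in residual variability can mean variance (residual SD √0.7 = 0.837) or SD (residual SD 0.7).

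*Shift at T1 only* (net shift = b):

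| b | t test | ANCOVA, variance −30% | ANCOVA, SD −30% |
|---|---|---|---|
| 0.1 | 6.1% | 6.6% | 7.3% |
| 0.2 | 9.5% | 11.4% | 14.2% |
| 0.3 | 15.2% | 19.7% | 26.2% |

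*Same shift at T0 and T1.* ANCOVA estimates the T1 shift minus slope × the T0 shift, so the net shift is b × (1 − slope). With equal SDs at the two visits, the slope equals the correlation: √(1 − 0.7) = 0.548 on the variance reading, and √(1 − 0.49) = 0.714 on the SD reading. For b = 0.3 the net shift is 0.3 × 0.452 = 0.136 SD, or 0.3 × 0.286 = 0.086 SD.

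| b | ANCOVA, variance −30% | ANCOVA, SD −30% |
|---|---|---|
| 0.1 | 5.3% | 5.2% |
| 0.2 | 6.3% | 5.7% |
| 0.3 | 7.9% | 6.6% |

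A T0 scored with the arm known therefore does not add to the T1 harm when the shift has the same direction; it offsets part of it. Only a T0 shift in the opposite direction would add, with net shift b × (1 + slope). That is a different mechanism, and nothing in the documents suggests it.

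**The case for a change.** The strongest case for a change is that an intended safeguard which is not written down cannot be followed consistently, audited or reported. The Fugl-Meyer is the primary outcome, its items need judgement, and the plan itself asks for careful control of bias. Two or three sentences would name the rater as blinded, put T0 before disclosure of allocation and keep each rater away from that patient's sessions and records. They would need no extra patients, visits or staff. Patients with up to moderate comprehension deficit are eligible ("Comprehension deficit, when present, should be minimal, mild or moderate"), so relying on patients not to disclose their treatment would be weak.

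What stands is the omission. The blinded party is not named, rater ignorance of the arm is not stated, and T0 is not ordered relative to allocation. It is also true that a shift at T1 alone could not be repaired in analysis, and that a more precise analysis reacts more to a given shift. The latter holds for any bias in any more precise analysis and is not a flaw of this plan.

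What does not stand is the step from silence to a biased comparison. That step needs rotation of roles, actual exposure of raters to arm-revealing material, and a shift of material size. The first is a reading, the second is conjecture, and the third is an assumed input.

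**Conclusion.** No change to the plan follows. The gap is one of missing detail. The single-blind label and the separation of treater and evaluator for each patient point to a blinded assessor, and a team carrying out the plan in that sense would obtain a sound primary comparison. The documents do not show that any rater will know the arm.

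The bias has no size that can be derived from the documents. The illustrative false-positive rates run from 5.2% to 26.2%, depending on an assumed shift of 0.1 to 0.3 SD, on which visits it affects, and on the analysis (t test or either reading of the ANCOVA gain). The upper end needs a shift of 0.3 SD at T1 alone and the residual-SD reading.

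The conclusion rests on reading the label and the role separation together as assessor blinding. It would change if there were evidence that raters attended their own patients' sessions or saw the allocation, and the documents contain none.
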